1.0 Purpose of the Investigation

1.1 Name of investigational device

Blackrock Microsystems NeuroPort Microelectrode Array System (Neuroport Array)

1.2 Intended use of the investigational device

In the proposed study, the efficacy of using NeuroPort Arrays (K070272) for chronic (>30 days) recording of neural signals in humans will be investigated. No modifications are being made to the Arrays as part of this investigation.

We will implant 2 NeuroPort Arrays in the motor cortex of individuals with limited or no ability to use both hands due to cervical spinal cord injury or brainstem or spinal stroke. The NeuroPort Arrays will be implanted for 1 year (+/- 30 days). Study participants will learn to control their neural signals (brain electrical activity) recorded from the NeuroPort Arrays in order to control a variety of external devices including virtual reality objects, a motorized prosthetic limb and a robotic arm exoskeleton in a safe environment. Demonstration of successful control of these devices will support our hypothesis that implantation of two NeuroPort Arrays allows for recording of sufficient neural information to control a complex BMI that can augment impaired motor functions.

For the proposed extension study, we are requesting a supplement to this IDE to allow for implantation duration of up to 5 years. This extension study will allow us to quantify BMI performance and signal quality over a longer duration.

The 510(k) approval for the NeuroPort Arrays describes the indications for use as:

“The intended use of the Cyberkinetics Neurotechnology Systems, Inc. NeuroPort Microelectrode Array System is for temporary (<30 days) recording and monitoring of brain electrical activity”. This 510(k) was purchased by Blackrock Microsystems from Cyberkinetics Neurotechnology Systems, Inc.

For the proposed investigation, the investigational indication for use would be:

“For chronic (>30 days) recording and monitoring of electrical activity from the motor cortex, in individuals with cervical spinal cord injury or stroke, to control external devices such as computers, assistive devices, and potentially robotic devices”.

The neural signals will be processed and recorded by the NeuroPort System as indicated by the current 510(k) approval (K090957). The NeuroPort System includes a patient cable which connects to the percutaneous pedestal connector of the NeuroPort Array, a neural signal processor, a front end amplifier/digitizer, and a computer and display monitor. The indications for use of the NeuroPort System are:

“The Blackrock NeuroPort Biopotential Signal Processing System supports recording, processing, and displaying of biopotential signals from user supplied

electrodes. Biopotential signals include: Electrocorticography (ECoG), electroencephalography (EEG), electromyography (EMG), electrocardiography (ECG), electrooculography (EOG), and evoked potential (EP).”

Because the NeuroPort System will be used as indicated by the 510(k), the IDE focuses solely on the NeuroPort Arrays.

1.3 Objectives of the clinical investigation

The proposed clinical investigation is a feasibility study directed toward:

Specific Aim 1: Investigate the safety and efficacy of using NeuroPort Arrays for chronic recording of neural activity from the motor cortex of individuals with upper limb impairments.

- Specific Aim 1a: Document the safety of using the NeuroPort Arrays for chronic recording of neural activity. Monthly neurological and physical examinations will be conducted and documented for the duration of the trial. Any serious adverse events that occur as part of this investigation will be reported in accordance with the FDA’s expedited reporting requirements.
- Specific Aim 1b: Characterize signal quality recorded with the NeuroPort Array during long term implantation in the motor cortex of individuals with tetraplegia. Primary measurements of signal quality include the number of units recorded by the array and the firing rate of single neurons measured during specific tasks (such as imagined hand movement) [6, 45, 46].

Specific Aim 2: Demonstrate that individuals with tetraplegia can learn to successfully control a variety of external devices and computer-driven tasks using signals recorded with two NeuroPort Arrays. We aim to achieve high-dimensional control of complex systems including both a virtual and robotic dexterous hand and arm to perform grasping and reaching tasks which are essential for activities of daily living. This will be measured over the duration of implantation by computing success rate for a given task as well as the amount of computer assist that is required.

Specific Aim 3: Use MEG to localize areas of the brain that can be voluntarily modulated. These results will be compared to pre-surgical mapping results with fMRI and provide additional information for planning the location of electrode implantation.

- Specific Aim 3a: At the optional follow-up MEG visits, we will use the same paradigms to localize areas of the cortex that can be voluntarily modulated to determine if BMI training has induced neuroplasticity. We expect the areas of cortex responsible for voluntary movement will be more strongly activated with more localized responses.

Specific Aim 4: Conduct a sleep study to measure the quantity and quality of sleep each night for a specified period of time to help clarify the role of sleep in motor learning.

This study will include a sleep diary and brain activity measured during sleep using EEG and/or intracortical recordings from the NeuroPort electrode arrays.

The aims remain the same for the proposed extension study, however we will have the opportunity to investigate these aims during the 1-5 year post-implant period. We also expect that we may see a decline in BMI performance over time as signal quality declines. This will be an opportunity to see if neuroplasticity, or novel training methods, can compensate for this degradation in performance.

1.4 Anticipated duration of the clinical investigation

It is expected that the study will last 3 years. If participants choose to enroll in the extension study, their total participation time could be up to 6 years.

2.0 Clinical Protocol

This section describes the core clinical protocol as already approved by the FDA and University of Pittsburgh IRB. Section 3.0 describes the clinical protocol for the proposed extension study.

2.1 Title of clinical protocol

Microelectrode Brain-Machine Interface for Individuals with Tetraplegia

2.1.1 Protocol number

University of Pittsburgh, PRO10080021

2.1.2 Version number and date

Version 10, November 12, 2013 (Exp Date: November 11, 2014)

2.2 Study design

2.2.1 General study design

This study is a prospective, non-randomized, open-label feasibility study that will be conducted at the University of Pittsburgh.

2.2.2 Study design schematic

Figure 2 illustrates the proposed study design. All procedures are discussed in detail in Section E 2.4.

[figure not shown]

Figure 2: Study Design Schematic

2.3 Subject selection

2.3.1 General characteristics of the proposed subject populations(s)

The subjects for this study will be individuals between the ages of 18-70 with limited or no ability to use both hands due to cervical spinal cord injury or brainstem or spinal stroke. Participants will be screened for a number of comorbidities to ensure their safety during participation. We are using adult subjects because this is a greater than minimal risk study and we want to ensure that the subject is mature enough to understand the tasks, as well as the risks involved in this study. Further, we want to ensure that the neuromotor system is fully developed prior to enrolling in this study. We will not be recruiting military or civilian personnel working for the Department of Defense (DOD).

2.3.2 Anticipated number of research subjects

A maximum of 10 participants will be enrolled in order to implant a maximum of 5 subjects. It is anticipated that we will implant no more than 1 subject every 6 months. Recruitment rates will be monitored by our DSMB. Because it is possible that a subject may enroll and then be determined to be ineligible for anesthesia and/or surgery, the maximum number of subjects enrolled may exceed the number implanted. Subjects will be enrolled as necessary to maintain the target number of subjects implanted. Recruitment will not begin until we have received IRB approval.

2.3.3 Inclusion criteria

- 1) limited or no ability to use both hands due to cervical spinal cord injury or brainstem or spinal stroke; The subjects must have less than or equal to grade 4 muscle strength in elbow extension and wrist extension and less than grade 2 strength in finger flexor and abduction on the contralateral side to the implant [47]. We will include both complete and incomplete subjects
- 2) subjects must report that they are unable to perform functional activities with the hand contralateral to implantation.
- 3) subjects must be over 1 year post-injury at time of implantation. In addition, subject must report no change in neurologic status (strength or sensation) for the previous 6 months.
- 4) age 18-70 years old. Participants outside this age range may be at an increased surgical risk and increased risk of fatigue during BMI training.
- 5) live within 1 hour of the University of Pittsburgh and be willing to travel to the University of Pittsburgh once per week for BMI training
- 6) expect to stay within 1 hour of and be willing to travel to the University of Pittsburgh for at least 18 months after enrollment
- 7) ability to communicate with the investigators verbally in English because of the need to follow instructions of the study team

- 8) show an understanding of the study goals and the ability to follow simple directions as judged by the investigators
- 9) have normal results on neuropsychological and psychosocial assessment (e.g., Wechsler Test of Adult Reading (WTAR) with a score of 90 or above and Brief Symptom Inventory (BSI-18) with a T-score less than 70); the WTAR measures intellectual functioning and the BSI-18 measures mental health; psychosocial health and support will be assessed by interview with the psychologist
- 10) able to activate distinct cortical areas during imagined or attempted movement tasks (i.e. hand movement and speaking or moving the mouth); this will be evaluated with functional magnetic resonance imaging (fMRI) as part of screening
- 11) must have a stable psychosocial support and caregivers who are able to perform the necessary daily care of the participant's skin and pedestal site; This requires that the subject identify a caregiver and a back up who have been in place for greater than 6 months and are able to provide needed physical and psychosocial support. This will be assessed by the study PI and neurosurgeon.
- 12) have a life expectancy greater than 12 months as assessed by the study investigator and neurosurgeon sub-investigator
- 13) documentation of informed consent is obtained from the participant or their legal representative

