2.3.4 Exclusion criteria

- 1) visual impairment such that extended viewing of a computer monitor would be difficult even with ordinary corrective lenses
- 2) presence of other serious disease or disorder that could affect ability to participate in this study (verified during pre-op anesthesia evaluation to determine surgical risk status)
- 3) recent history of pressure sores that could be exacerbated by 1-2 days of bed rest
- 4) metallic implants that would prohibit the subject from having a fMRI scan; spinal fixators are generally non-ferrous and would not exclude someone from participating in the study
- 5) individuals who have any type of implantable generator such as a pacemaker, spinal cord stimulator, cochlear implant, deep brain stimulator, vagus nerve stimulator, or defibrillator
- 6) women of childbearing age who are pregnant, lactating, or plan to become pregnant during the next 25 months
- 7) allergy to contrast medium or kidney failure that could be exacerbated by contrast agent (for MRI)
- 8) receiving medications (such as sedatives) chronically that may retard motor

coordination and cognitive ability

- 9) individuals who require routine MRI, therapeutic ultrasound, or diathermy
- 10) individuals with osteomyelitis
- 11) having a severe skin disorder that causes excessive skin sloughing, lesions or breakdown of the scalp
- 12) history of myocardial infarction or cardiac arrest or with intractable cardiac arrhythmias
- 13) individuals with an implanted hydrocephalus shunt
- 14) individuals who have had a stroke cause by a surgical procedure
- 15) active infection(s) or unexplained fever (verified during pre-op anesthesia evaluation to determine surgical risk status)
- 16) consuming more than 1 alcoholic beverage per day on average
- 17) receiving chronic oral or intravenous steroids or immunosuppressive therapy
- 18) active cancer within the past year (other than adequately treated basal cell or squamous cell skin cancer) or require chemotherapy
- 19) uncontrolled insulin dependent diabetes mellitus
- 20) uncontrolled autonomic dysreflexia (for those with spinal cord injury)
- 21) history of seizures
- 22) attempted suicide in the past 12 months

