It is the responsibility of the principal investigator (PI) that each subject being considered for participation in the study be given a full explanation of the protocol. Informed consent is mandatory after adequate explanation of the objectives, methods, anticipated benefits, and potential risks of the study before any study specific procedures are performed. The informed consent form must include the required eight basic elements. Informed consent will, consistent with site institutional policies and FDA regulations (21CFR, Part 50), be obtained in the following manner.

A meeting will be held with the investigator, potential study participant, his/her family member or primary caregiver, and if required (i.e., if not the family member/primary caregiver), the subject's legal representative that is authorized to sign for the subject. The investigator will discuss the study with all those present. The informed consent form will be reviewed in detail and a discussion of the nature and duration of the study as well as the anticipated risks and benefits will take place. The subject and family member/primary caregiver will be encouraged to ask questions and these questions will be answered. The subject will be encouraged to take additional time, if necessary, to consider participation before signing or having the informed consent signed by their legal representative.

The family member/primary caregiver is agreeing to support the subject in their chronic care environment. This support includes reading and following the instructions for daily wound monitoring and weekly cleaning designed to minimize the risk of infection. The family member/primary caregiver and the subject will also be responsible for informing any other caregivers or nursing staff about the subject's participation in the study and the steps required to minimize the risk of infection.

Once written informed consent is obtained, the subject is enrolled in the study and is assigned a subject ID. A physician-investigator will then verify the eligibility of the subject by assessing all of the eligibility criteria. The subject's muscle strength will be tested by a physician-investigator or therapist. Two additional screening procedures will be conducted after informed consent, but prior completing the study procedures.

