2.4.2 Experimental procedures

Pre-surgical procedures and electrode implantation will occur within 6 months after the subject undergoes screening procedures. We will work with each individual to determine the optimal testing schedule. We will photograph or videotape portions of the experimental sessions. Appropriate UPMC permission will be obtained as needed for any photographs or videotaping of participants. All experimental procedures are described below.

Demographic and Medical History Questionnaire:

The subject will be asked to provide basic demographic information (age, weight, height, etc.) via self-report. We will also ask questions about their medical history including the date of injury or diagnosis and their current level of function. Finally, we will ask questions related to improvement of quality of life and BMI technology. A complete copy of the questionnaire is included with the Case Report Forms in Appendix I. This questionnaire is expected to take less than 30 minutes to complete and can be completed at any of the study visits.

Pre-surgical Magnetoencephalography (MEG) Testing:

Subjects will participate in a MEG scan prior to surgery where they will be asked to perform simple imagined or attempted movements which will provide additional data related to the ideal site for electrode implantation. Similarly, they may be asked to observe actions performed by others. These actions will be simple movements such as hand grasp or tongue movement. As part of the standard protocol for MEG testing, we may attach additional sensors (using tape or an adhesive) to record head position, electroencephalography (EEG), electrocardiography (EKG), electromyography (EMG), or electro-oculography (EOG). EEG is an additional measurement of neural activity. The other recordings allow us to correct for noise sources or head movement. MEG and all of the related recordings are completely non-invasive. The MEG test allows us to measure cortical sources of activity with high spatial and temporal resolution. MEG testing

following the same procedure will be performed again after BMI testing is completed to determine if plasticity has been induced. For example, we would expect the sources responsible for imagined movement to be stronger following BMI training. The pre-surgical MEG session is expected to take less than 2 hours. All MEG scans will take place at the UPMC Brain Mapping Center at UPMC Presbyterian Hospital.

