2.5 Study outcome evaluations

2.5.1 Study endpoints

The NeuroPort Arrays will be removed 1 year (+/- 30 days) after implantation. A participant will be considered a success for safety if the device is not explanted for safety reasons during the 12-month post-implant evaluation. If the subject experiences treatment resistant (serious) adverse events, he or she will be withdrawn and the arrays will be explanted early (See Section E 2.4.4). The study may also end early if the subject is non-compliant (See Section E 2.4.4).

We believe it is possible that a participant will not want the array removed. If the participant wants the NeuroPort Arrays to stay in, the study PI and neurosurgeon will assess whether this is acceptable. This decision will be based on whether or not the participant is at increased risk by leaving the arrays in and whether the device is still measuring neural activity that is sufficient for brain control. We will consult our DSMB if conflicts arise. One participant in the BrainGate trial has had a NeuroPort Array implanted for more than 1000 days without adverse event [9]. If the NeuroPort Arrays remain implanted for more than 1 year, we will continue to perform clinical follow-up as described in the current protocol. We may also continue brain-machine interface testing although the frequency of the training sessions may be reduced. We will remove the NeuroPort Arrays at anytime as directed by the participant, or as dictated by their clinical condition.

If the participant wishes to leave the NeuroPort Array implanted, but the study PI and neurosurgeon do not feel that it is in their best interest, the participant will be counseled that they should have the NeuroPort Array removed and that not doing so could result in clinically significant adverse events. They will also be informed that brain-machine interface training will not continue. The consent form includes a statement that participants will be financially liable for any medical care resulting from complications of not having the device removed upon instruction of the study PI. We will however allow participants to have the device removed at anytime and the explantation costs would be covered by this study.

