3.3.3 Inclusion criteria

- 1) Participant in PRO10080021 study (IDE G100298) who is at least 6 months post-implant
- 2) Have no unresolved significant adverse events during participation in PRO10080021
- 3) Have demonstrated at least 4-dimensional control of a virtual or real robotic arm during participation in PRO10080021
- 4) Have a stable psychosocial support and caregivers who are able to perform the necessary daily care of the participant's skin and pedestal site; This requires that the subject identify a caregiver and a back up who have been in place for greater than 6 months and are able to provide needed physical and psychosocial support. This will be assessed by the study PI and neurosurgeon.
- 5) Age 18-70 years old at the time of consent and planned explant
- 6) Have a life expectancy greater than 12 months as assessed by the study principal investigator and neurosurgeon sub-investigator
- 7) Live within 1 hour of the University of Pittsburgh, or be willing to travel there, once per week for BMI testing
- 8) Interested in having the NeuroPort arrays remain in place for 6 months to 4 years beyond the 1 year implantation that is part of PRO10080021. Participants can

decide to extend the implantation for any duration between 6 months and 4 years. This can be decided at any point during the study.

- 9) Participation is not expected to have an adverse effect on mental well-being as judged by the rehabilitation psychologist
- 10) Documentation of informed consent is obtained from the participant or their legal representative

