3.4.2 Experimental procedures

This study is an optional extension to PRO10080021. Consent and screening for this study may occur as early as 6 months after implant and up to 13 months after implant (the maximum duration allowed in the original protocol). BMI testing will occur as described in the original protocol with similar ongoing clinical monitoring and follow-up as described below:

Brain-Machine Interface (BMI) Training/Testing:

Neural recording will be conducted for the duration of implantation. The recorded neural data will be used to operate a BMI system that allows the participant to control a computer cursor, virtual object, or assistive device. While the NeuroPort Arrays are implanted, we will conduct BMI training for up to 8 hours per day for up to 5 days per week. At least 1 session per week will be attempted while the array is implanted. BMI testing may occur at the University of Pittsburgh, UPMC, or in the participant's home. Rest, meals, and other breaks will be scheduled as needed. We may not conduct training sessions every day. This will be determined by the research staff and the subject. Also, we may not conduct testing sessions for up to 8 weeks per year. Since participants will have already completed 1 year of testing, we hope to minimize the burden on participants while still collecting valuable data related to signal quality and BMI control. The subject will go no longer than 3 weeks between testing sessions. This will assure that the study team can continue to monitor the wound site and well being of the participant.

At the beginning of each BMI testing session, an investigator will connect the Patient Cable to the Patient Pedestal. We may also record neural activity using EEG electrodes which are placed on the scalp in order to measure larger networks of brain activation. There are two types of behavioral tasks that the subject will participate in as part of the BMI training/testing: 1. Open-loop and 2. Closed Loop. These tasks are the same as described in Section 2.4.2.

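### On the longest schedule the core protocol permits, the 18-month availability criterion ends about 1 month before explant and 2 months before the last planned clinical visit, and the 12-month life-expectancy criterion has no start point.

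*Combined protocol and SAP*

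**What the plan says.** All places are in the combined protocol and SAP.

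- **Local availability (2.3.3, item 6):** "expect to stay within 1 hour of and be willing to travel to the University of Pittsburgh for at least 18 months after enrollment".
- **Start of the clock (2.4.1):** "Once written informed consent is obtained, the subject is enrolled in the study and is assigned a subject ID". Strength testing, the neuropsychological examination and the fMRI follow consent.
- **Wait to implant (2.4.2):** "Pre-surgical procedures and electrode implantation will occur within 6 months after the subject undergoes screening procedures".
- **Implant duration (2.5.1):** "The NeuroPort Arrays will be removed 1 year (+/- 30 days) after implantation". Section 3.4.2 confirms the ceiling: "up to 13 months after implant (the maximum duration allowed in the original protocol".
- **After explant (2.4.3):** clinical visits are expected at 1 and 4 weeks (+/- 3 days). Optional MEG sessions are planned at 2 weeks, 6 weeks and 3 months, within 6 months of the end of BMI training. Section 4.1 undertakes to follow participants for at least three weeks after explant.
- **Pregnancy exclusion (2.3.4, item 6):** "women of childbearing age who are pregnant, lactating, or plan to become pregnant during the next 25 months".
- **Life expectancy, core (2.3.3, item 12):** "have a life expectancy greater than 12 months as assessed by the study investigator and neurosurgeon sub-investigator".
- **Life expectancy, extension (3.3.3, item 6):** "Have a life expectancy greater than 12 months as assessed by the study principal investigator". Item 5 of the same list ties the age limit to the planned explant as well as to consent. Item 8 lets the participant choose 6 months to 4 years beyond the first year.

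**The concern.** An availability criterion and a life-expectancy criterion should reach as far as the follow-up they are meant to secure. Here each carries a fixed number of months that does not follow from the schedule elsewhere in the protocol, and only item 6 says where its count begins. A candidate could meet both criteria and still plan to be away at explant or the wound checks after it, or have a prognosis that ends before the 12-month assessment that defines safety success. With at most 5 implanted participants, each explant, wound check and endpoint assessment counts.

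**Working it through.** **Inputs.** Month 0 is enrollment at consent. The wait to implant is 0 to 6 months. Implantation lasts 12 months +/- 30 days, and 30 days is 0.99 month (30 / 30.44). The last planned clinical visit is 4 weeks after explant (28 / 30.44 = 0.92 month), and the last planned MEG session is 3 months after. The MEG window closes 6 months after the end of training, taken here as the explant date. Time between consent and the end of screening is not stated and is set to 0; any such time adds to every figure.

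**The plan's own longest horizon.** The 25 months in the pregnancy exclusion equals wait + longest implantation + MEG window: 6 + 13 + 6 = 25. The 6-year total with extension in 1.4 matches the same way: 6 + 60 + 6 = 72 months. The documents do not show either sum, so this derivation is an inference.

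**Availability criterion.** Explant month = wait + implant duration; later events are added to it.

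| Wait | Implant duration | Explant | 4-week visit | 3-month MEG | MEG window closes |
|---|---|---|---|---|---|
| 6 | 12 + 30 days | 19.0 | 19.9 | 22.0 | 25.0 |
| 6 | 12 | 18.0 | 18.9 | 21.0 | 24.0 |
| 5 | 12 + 30 days | 18.0 | 18.9 | 21.0 | 24.0 |
| 4 | 12 + 30 days | 17.0 | 17.9 | 20.0 | 23.0 |
| 4 | 12 | 16.0 | 16.9 | 19.0 | 22.0 |
| 0 | 12 | 12.0 | 12.9 | 15.0 | 18.0 |

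Against 18 months, the longest permitted schedule is short by 19.0 - 18 = 1 month for explant, 19.9 - 18 = about 2 for the 4-week visit, 4 for the last planned MEG session and 7 for the close of the MEG window.

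The longest wait for which 18 months is still enough:

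- Explant: 18 - 12 = 6 months (12-month implantation), or 18 - 12.99 = 5.0 (with the extra 30 days).
- 4-week visit: 18 - 12 - 0.92 = 5.1 months, or 18 - 12.99 - 0.92 = 4.1.
- 3-month MEG: 18 - 12 - 3 = 3 months, or 18 - 12.99 - 3 = 2.0.

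**Life expectancy, core.** The 12-month post-implant endpoint falls at wait + 12, that is, months 12 to 18 from screening. A prognosis only just above 12 months, counted from screening, can therefore end up to 6 months before it. Counted from implantation, it reaches the endpoint but not a 13-month explant, nor the 4-week visit after a 12-month implantation (12 + 0.92 = 12.9).

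**Life expectancy, extension.** Consent comes 6 to 13 months after implant (3.4.2). For the longest stay, explant at about month 60 is 60 - 13 = 47 to 60 - 6 = 54 months after consent, so a 12-month minimum is 35 to 42 months short. For the shortest stay (explant at month 18) it is 18 - 13 = 5 to 18 - 6 = 12 months after consent, and the criterion reaches explant.

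**The case against.** Much of the case on the other side stands. Six months is a ceiling on the wait, so it should not be read as the typical case. Eighteen months equals 6 + 12: even after the longest wait it covers the 12-month safety endpoint, a 12-month explant and the weekly data for Aims 1b and 2. Explant itself is missed only when a wait of more than about 5 months coincides with use of the 30-day allowance. The largest shortfalls, 4 and 7 months, concern MEG visits that 2.4.3 makes optional and that 2.4.2 says are not the main priority. The pregnancy exclusion protects against imaging and surgical risk (4.1), so its 25 months need not equal the residence period. Section 2.3.4 separately excludes serious disease that could affect participation, and the pre-operative evaluation checks this up to 30 days before surgery; few enrollees would have a prognosis near 12 months. The longest extension shortfall applies only to someone who chooses the full stay.

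A reader might go further and infer that eligible participants can be expected to leave before explant, or that one in five implanted participants would be lost. The documents do not support either reading. Both criteria are minima and do not make departure the likely course. Someone who moves at month 18 has already supplied the endpoint, and moving more than an hour away does not prevent a return for surgery or a wound check.

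These arguments do not close the gap at the edge. No other section extends the 18 months to the post-explant clinical visits, or says from when life expectancy is counted.

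**Conclusion.** The point holds as a minor mismatch at the edge of the permitted schedule. Item 6 is adequate for early implants and too short for late ones, and what it then fails to secure is the post-explant clinical follow-up and, in the extreme case, explant itself. The life-expectancy criteria are the less well defined of the two: without a start point, nobody can say whether item 12 of the core list reaches the endpoint that defines success, and the extension's version matches only short stays.

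The result assumes no time between consent and the end of screening (more would widen the gap), training that ends at explant, and life expectancy counted from about screening. The documents give no distribution of waiting times, so how often the edge case would arise cannot be estimated from them.

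**What to change.** In 2.3.3 item 6, replace 18 months with at least 20 months after enrollment, or with 25 if the optional MEG window is to be covered. Alternatively, define the period as running from implantation through the 4-week post-explant visit, which removes the dependence on the wait.

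In 2.3.3 item 12 and 3.3.3 item 6, state the date from which life expectancy is counted. The sponsor should reconcile the first with the 12-month post-implant endpoint and the second with the participant's planned explant date, as item 5 of the extension list already does for age. The clinical threshold remains the sponsor's decision.

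The cost is a wording change to three criteria. A few candidates who plan to move, or whose prognosis is limited, would no longer qualify.
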